11.2 Monitoring and Quality Assurance

Independent monitors will monitor the study in each country according to a pre-specified monitoring plan. The monitors are trained in GCP and will be trained on study specific tasks and processes. As part of George Clinical's Quality Management Strategy monitor oversight will be implemented through regular documentation reviews and co-monitoring activities.

11.3 Amendments

A 'substantial amendment' is defined as an amendment to the terms of the ethics committee (METC) application, or to the protocol or any other supporting documentation, that is likely to affect to a significant degree:

- the safety or physical or mental integrity of the subjects of the trial;
- the scientific value of the trial;
- the conduct or management of the trial; or
- the quality or safety of any intervention used in the trial.

All substantial amendments will be notified to the METC and to the competent authority.

Non-substantial amendments will not be notified to the accredited METC and the competent authority, but will be recorded and filed by the sponsor.

11.4 Annual progress report

The sponsor's principal investigator and project leader will submit a summary of the progress of the trial to the accredited METC once a year. Information will be provided on the date of inclusion of the first subject, numbers of subjects included and numbers of

subjects that have completed the trial, serious adverse events/ serious adverse reactions, other problems, and amendments.

11.5 End of study report

The sponsor will notify the accredited METC and the competent authority of the end of the study within a period of 90 days. The end of the study is defined as the last patient's last visit.

In case the study is ended prematurely, the sponsor will notify the accredited METC and the competent authority within 15 days, including the reasons for the premature termination.

Within one year after the end of the study, the principal investigator and project leader from the UMCG will submit a final study report with the results of the study, including any publications/abstracts of the study, to the accredited METC and the Competent Authority.

11.6 Public disclosure and publication policy

The study will be registered at clinicaltrials.gov or equivalent trial registries. Publication policy is in agreement with international regulations. Nor the sponsor, nor the principal investigator has a right of veto regarding the way of publishing the results.

12. STRUCTURED RISK ANALYSIS

12.1 Potential issues of concern

a. Level of knowledge about mechanism of action

The Sodium glucose co-transporter 2 (SGLT2), located in the proximal tubule of the kidney, is an effective transporter system which is responsible for the nearly complete reabsorption of glucose in order to maintain appropriate glucose levels. Each glucose molecule that is reabsorbed is accompanied by reabsorption of a sodium molecule in a 1:2 ratio. SGLT2 inhibitors reversely inhibit the SGLT-2 transporter which leads to enhanced glucose and sodium excretion and a reduction in plasma glucose and Hba1c. The effects of dapagliflozin on the SGLT2 transporter are well characterized and sufficient knowledge is available about the mechanisms of action.^{14, 15}

b. Previous exposure of human beings with the test product(s) and/or products with a similar biological mechanism

Twelve phase 3 randomized controlled clinical trials were conducted involving more than 6000 patients with type 2 diabetes of whom ~4000 were treated with dapagliflozin. Eleven studies were 24-weeks in duration with extension in 6 studies up to 78 weeks. One study was 52 weeks in duration with extension of another 52 weeks.

Another SGLT2 inhibitor is registered in the US and filed for registration in Europe (canagliflozin). A third SGLT2 inhibitor (empagliflozin) is filed for registration in the US and Europe. In addition, a number of other SGLT-2 inhibitors are in various stages of clinical development.

c. Can the primary or secondary mechanism be induced in animals and/or in ex-vivo human cell material?

Various animal models and cell lines are available to study the effect of SGLT2 inhibitors in more detail at a tissue/cell level.

d. Selectivity of the mechanism to target tissue in animals and/or human beings

SGLT2 is highly localized to the kidney and major effects are expected to be related to glycosuria and natriuresis.

e. Analysis of potential effect

In placebo controlled clinical trials the following adverse reactions have been identified:

- *Infections and infestations*: vulvovaginitis, balanitis and genital infections, urinary tract infections (Common)

- *Metabolism and nutrition disorders*: Hypoglycemia; volume depletion (uncommon)
- *Gastrointestinal disorders*: Constipation (uncommon)
- *Musculoskeletal*: Back pain (Common)
- *Renal and urinary disorders*: Dysuria; Polyuria (Common); Nocturia (uncommon)

Common (>1/100 to <1/10) and uncommon (>1/1000 to <1/100)

Few adverse events led to discontinuation of treatment and adverse events were balanced across study groups. The most commonly reported events leading to discontinuation in patients treated with dapagliflozin 10 mg/day were increased blood creatinine (0.4%), urinary tract infections (0.3%), nausea (0.2%), and rash (0.2%). It should be noted that the transient rise in serum creatinine may reflect a reduction in intra-glomerular pressure which may be associated with long-term structural renal protection.

A pooled analysis of 3152 patients who received dapagliflozin in doses between 2.5 and 10 mg/day showed that the incidence of urinary tract infection was increased with dapagliflozin dosage. Most diagnosed infections were mild to moderate and responded to standard antimicrobial treatment.¹⁶

Safety data in patients with diabetic kidney disease has been generated in phase 3 trials and demonstrated no additional side effects compared to type 2 diabetes patients without kidney disease. Given the SGLT2i mode of action no further safety issues are anticipated in non-diabetic CKD patients as compared to generally more vulnerable diabetic kidney disease patients included in the past phase 3 studies.

Overdose:

Dapagliflozin did not show any toxicity in healthy subjects at single oral doses up to 500 mg (50 times the dose aimed to be used in the present study). These subjects had detectable glucose in the urine for a dose-related period of time (at least 5 days for the 500 mg dose) with no reports of dehydration, hypotension, or electrolyte imbalance and with no clinically meaningful effect on QT_c interval. The incidence of hypoglycaemia was similar to placebo. In clinical studies where once-daily dosing of up to 100 mg dapagliflozin were administered for 2 weeks in healthy subjects and type 2 diabetes subjects the incidence of hypoglycaemia was slightly higher than placebo and was not dose-related.

f. Pharmacokinetic considerations

In *in-vitro*- studies, dapagliflozin neither inhibited cytochrome P450, CYP2A6, CYP2B6, CYP2C8, CYP2C9, CYP2C19, CYP2D6, CYP3A4 nor induces CYP1A2, CYP2B6, CYP3A4. Therefore, dapagliflozin is not expected to alter the metabolic clearance of coadministered medicinal products that are metabolized by these enzymes.

Interaction studies conducted in healthy subjects, using mainly a single dose design, suggest that the PK of dapagliflozin is not altered by metformin, pioglitazone, sitagliptin, glimepiride, hydrochlorothiazide, bumetanide, valsartan, or simvastatin.

g. Study population

The enrolled population is in a stable condition and no unexpected serious adverse events are foreseen.

h. Interaction with other products

See f

i. Predictability of effect

Efficacy is monitored by measuring albuminuria / blood pressure / Hba1c which are accepted and accurate surrogates to evaluate efficacy.

j. Can effects be managed?

Patients are regularly monitored and asked about adverse effects of urinary tract infections or infestations. As reported above, dapagliflozin administration is associated with an increased risk of infections which can be managed with standard antimicrobial treatment.¹⁶

12.2 Synthesis

The available data show that dapagliflozin decreases HbA1c, blood pressure and body weight in patients with type 2 diabetes. The drug received marketing approval from the EMA and is registered in various EU-countries. Dapagliflozin increases incidence of urinary tract infections. This adverse effect led in rare instances to treatment discontinuation and is manageable with standard antimicrobial treatment.

The DIAMOND trial

A study to assess the Renoprotective Effects of the SGLT2 Inhibitor Dapagliflozin in Non-Diabetic Patients with Proteinuria: a Randomized Double Blind 6-Weeks Cross-Over Trial

STATISTICAL ANALYSIS PLAN

Version 1.5

13 September 2019

Prepared by:

[name]

[name]

[name]

NCT03190694

Approved by: [name]

Role: Principal Investigator

Signature: 

Date: 16 Sep 2019

Approved by: [name]

Role: co-Principal Investigator

Signature: 

Date: September 18, 2019

Approved by: [name]

Role: Head of Statistics, Australia, The George Institute for Global Health

Signature: _____

Date: 13 September 2019

1. Study synopsis

Despite optimal treatment with renin-angiotensin-aldosterone-system (RAAS) inhibitors, many patients with non-diabetic kidney disease show progressive kidney function loss, which is associated with high residual albuminuria. Novel treatment strategies are therefore required to further decrease albuminuria and to slow kidney function decline.

Dapagliflozin is a sodium-glucose transport (SGLT2) inhibitor and inhibits the reabsorption of glucose and sodium in the proximal tubule. The increased natriuresis following dapagliflozin administration normalizes tubuloglomerular feedback resulting in a reduction in intra-glomerular hypertension, which is in turn manifested by acute reductions in glomerular filtration rate and albuminuria. Since many etiologies of non-diabetic nephropathy are characterized by intraglomerular hypertension, we hypothesize that dapagliflozin acutely decreases GFR and albuminuria in patients without diabetes at risk of progressive kidney function loss via a glucose independent hemodynamic mechanism.

SGLT2 has a plausible therapeutic potential in individuals with non-diabetic nephropathy at risk of renal progression, and are likely to be well tolerated. Exploring the beneficial effects of these agents in non-diabetic proteinuric kidney disease may pave the way for a new indication for this class of drugs. In addition, trials in non-diabetic kidney disease may help to further characterize the non-glucose dependent effects, which may help to differentiate SGLT2i from other glucose lowering agents.

2. Study objectives

Our aim is to investigate two interventions that will be administered to the enrolled patients: Dapagliflozin 10 mg/day and matched placebo.

2.1. Primary Objective

- To assess the change baseline in 24-hr proteinuria with dapagliflozin for six weeks relative to placebo treatment in patients with non-diabetic kidney disease and proteinuria > 500 mg/day on stable ACEi or ARB treatment

2.2. Secondary Objectives

- To assess the effect of dapagliflozin 10 mg/d compared to placebo on Glomerular Filtration Rate (GFR) using iohexol clearance.
- To assess the effect of dapagliflozin 10 mg/d compared to placebo on systolic/diastolic blood pressure
- To assess the effect of dapagliflozin 10 mg/d compared to placebo on body weight
- To assess the effect of dapagliflozin 10 mg/d on selected neurohormones/biomarkers:
 - Hormones of the RAAS (plasma and urine)
 - Natriuretic peptides
 - Urinary adenosine
 - Co-peptin
 - Immunoglobulin G (plasma and urine)
- To characterize the safety of dapagliflozin vs. placebo by determining the number of hypoglycemic episodes between groups, and serious adverse events.

3. Study design

Randomized placebo controlled double blind cross-over trial. Eligible participants will be randomly assigned to one of the two treatment orders: placebo-dapagliflozin *or* dapagliflozin-placebo. Each treatment period lasts 6 weeks followed by a 6 week wash-out period to avoid cross-over effects. Patients will have their study visit in the morning in fasted condition.

3.1. General Design and Plan

A double blind randomized placebo controlled cross-over study will be conducted in subjects with Chronic Kidney Disease aged between 18 and 75 years, proteinuria levels between 500 and 3500 mg/24-hour, and an eGFR \geq 25 ml/min/1.73m² will be enrolled. Patients with type 1 or type 2 diabetes, polycystic kidney disease, glomerulonephritis with flares (lupus or anti-neutrophil cytoplasmic antibodies (ANCA) associated vasculitis) or ongoing active renal inflammation will be excluded. Since each subject is his/her own control, this design requires fewer patients as compared with a parallel study design. A wash-out period after each treatment period has been included in the design to avoid cross-over effects.

The study will consist of a screening visit, a 4-week run-in phase for those subjects not on stable ACEi/ARB treatment, 2 consecutive 6-week double blind treatment periods separated by 6-week wash-out period. Subjects will be randomly assigned to one of the treatment orders as depicted in figure 1.

Figure 1: Study design

Screening	Run-in 4 weeks	Placebo 6 weeks	Wash-out 6 weeks	Dapa 10 mg 6 weeks	Wash-out 6 weeks
Screening	Run-in 4 weeks	Dapa 10 mg 6 weeks	Wash-out 6 weeks	Placebo 6 weeks	Wash-out 6 weeks

3.2. Sample Size

Sample size calculations estimated 50 patients completing the study would provide 80% power to detect a 25% reduction in albuminuria. Assuming that approximately 5% of patients will discontinue the study prematurely, we intend to enrol 53 subjects. This calculation assumed a conservative standard deviation of 0.7 in log transformed proteinuria (within-subject standard deviation of 0.475) in order to detect (with alpha at 0.05) at least the 25% reduction in mean albuminuria (i.e, delta=0.288 on the log-transformed proteinuria scale) in dapagliflozin compared to placebo.

4. Study population

Male and female subjects with Chronic Kidney Disease aged between 18 and 75 years, proteinuria levels between 500 and 3500 mg/24-hour, and an eGFR ≥ 25 mL/min/1.73m² will be enrolled. Patients with type 1 or type 2 diabetes, polycystic kidney disease, glomerulonephritis with flares (lupus or anti-neutrophil cytoplasmic antibodies (ANCA) associated vasculitis) or ongoing active renal inflammation will be excluded. Patients have to be treated with a stable dose of an ACEi or ARB for at least 4 weeks prior to enrolment.

The study population will be selected from the outpatient clinical from hospitals based in the Netherlands (Groningen, Almelo, Amsterdam), Canada, (Toronto, Calgary, Vancouver) and Malaysia (Kuala Lumpur) with the following pre-specified inclusion and exclusion criteria.

Inclusion criteria

- Age ≥ 18 and ≤ 75 years
- Diagnosis of IgA nephropathy, focal segmental glomerulosclerosis, or membranous nephropathy. A biopsy proven diagnosis is not a prerequisite for participation in this study.
- Urinary protein excretion > 300 mg/g and ≤ 3500 mg/g in a 24-hr urine collection
- eGFR ≥ 25 mL/min/1.73m²
- On a stable dose of an ACEi or ARB for at least 4 weeks prior to randomization
- Willing to sign informed consent
- Women of Child-Bearing Potential (WOCBP):
 - WOCBP must be using an acceptable method of contraception to avoid pregnancy throughout the study and for up to 4 weeks after the last dose of study drug in such a manner that the risk of pregnancy is minimized.
 - WOCBP must have a negative serum or urine pregnancy test result (minimum sensitivity 25 IU/L or equivalent units of HCG) within 0 to 72 hours before the first dose of study drug.
 - Women must not be breast-feeding.

WOCBP comprises women who have experienced menarche and who have not undergone successful surgical sterilization (hysterectomy, bilateral tubal ligation, or bilateral oophorectomy) or who are not post-menopausal.

Exclusion criteria

- Diagnosis of type 1 or type 2 diabetes mellitus
- Urinary protein excretion > 3500 mg/day
- Autosomal dominant polycystic kidney disease
- Indication for immunosuppressants as per the treating physician's judgment.
- Treatment with corticosteroids or immunosuppressant within the last 6 months
- Active malignancy aside from treated squamous cell or basal cell carcinoma of the skin.
- Any medication, surgical or medical condition which might significantly alter the absorption, distribution, metabolism, or excretion of medications including, but not limited to any of the following:
 - History of active inflammatory bowel disease within the last six months;
 - Major gastrointestinal tract surgery such as gastrectomy, gastroenterostomy, or bowel resection;
 - Gastro-intestinal ulcers and/or gastrointestinal or rectal bleeding within last six months;
 - Pancreatic injury or pancreatitis within the last six months;
 - Evidence of hepatic disease as determined by any one of the following: ALT or AST values exceeding 3x ULN at inclusion visit, a history of hepatic encephalopathy, a history of esophageal varices, or a history of portocaval shunt;
 - Evidence of urinary obstruction or difficulty in voiding at screening
- History of severe hypersensitivity or contraindications to dapagliflozin
- Subject who, in the assessment of the investigator, may be at risk for dehydration or volume depletion that may affect the interpretation of efficacy or safety data
- Participation in any clinical investigation within 3 months prior to initial dosing.
- Donation or loss of 400 ml or more of blood within 8 weeks prior to initial dosing.
- History of drug or alcohol abuse within the 12 months prior to dosing, or evidence of such abuse as indicated by the laboratory assays conducted during the screening.
- History of noncompliance to medical regimens or unwillingness to comply with the study protocol.
- Any surgical or medical condition, which in the opinion of the investigator, may place the patient at higher risk from his/her participation in the study, or is likely to prevent the patient from complying with the requirements of the study or completing the study.
- Pregnancy or breastfeeding

- WOCBP who are unwilling or unable to use an acceptable method to avoid pregnancy for the entire study period and up to 4 weeks after the last dose of study drug.

4.1. Patients recruitment, eligibility and measurements

The target population will be invited for screening. Subjects who meet all entry criteria and who are already on a stable dose (no changes in dose or type of drug) of ACEis or ARBs for at least 4 weeks proceed directly to randomization. Subjects who had their ACEi or ARB medication changed during the preceding 4 weeks of the screening visit proceed to a run-in phase during which the type and dose of these drugs are stabilized. Subjects will be randomly assigned to one of the two treatment orders as depicted in figure 1. Each treatment period lasts 6 weeks followed by a 6 week wash-out period to avoid cross-over effects. Subjects will have their study visit in the morning in fasted condition.

Subjects will be instructed to take the study medication once daily, in the morning, except on study days; on those days, the study drug will be taken after the patient visit.

Measurements

- During the double blind treatment period, and wash-out period patients will collect a 24-hour urine collection at each visit for measurement of 24-hour protein, albumin, glucose, sodium, potassium, creatinine, and urea excretion. Twenty-four hour urine collections will be performed at:
 - Screening visit
 - Day 1, week 3, and week 6 (last day on treatment) of each treatment period
- Office systolic and diastolic blood pressure measurements will be performed at day 1, week 3 and 6 (last day on treatment) of each treatment period
- Vital signs (heart rate and body weight) and blood will be sampled for measurement of HbA1c, glucose, complete blood count, plasma albumin, RAAS biomarkers, natriuretic peptides, co-peptin, neurohormones at day 1, week 3 and 6 of each treatment period.
- Blood and urine samples will be stored for future exploratory biomarker analyses to study the effect of dapagliflozin in this study population.

4.2. Randomization and blinding

Treatment sequence of dapagliflozin and placebo will be randomized. A computer generated randomized code generated by the sponsor will be used. The pharmacy of each participating centre will store the randomization code. Unblinding is not to be performed for any reason, other than an emergency where unblinding is required.

5. Statistical analysis

The flow of patients through the study (screened, fulfilled eligibility criteria, excluded, randomized and potential drop-outs) will be graphically displayed in a CONSORT diagram. Baseline characteristics will be described by sequence group. All tests are to be two-sided with nominal level alpha set at 5%.

Descriptive statistics will be used to analyse the means and distribution between all the study variables. The means of the normal distributed variables will be compared with the student T-test and non-parametric tests (Mann-Whitney U-test for continuous and Chi-Square test for categorical variables) will be used for the variables that present a particularly skewed distribution.

The base-case analyses of the treatment effects will be unadjusted (with the exception of the period effect).

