7.1.3 Other study parameters (if applicable)

- Number of hypoglycaemic episodes
- Serious Adverse Events
- Drug related adverse events (causality to investigational product assessed by research physician).

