9.3 Other study parameters

Descriptive statistics will be used to analyse the means and distribution between all the study variables. The means of the normal distributed variables will be compared with the student T-test and non-parametric tests (Mann-Whitney U-test for continued and Chi-Square test for nominal variables) will be used for the variables that do not follow a normal distribution. Missing values will be imputed using multiple imputation techniques. Before introducing multiple imputation techniques the pattern of missing values will be examined. If the pattern of missing values indicate that missing values occur randomly a PROC MI statement in SAS will be implemented to impute missing values.

In case patients require rescue medication this will be recorded in the database. During the data-analysis sensitivity analyses will be conducted by adding an additional covariate in the mixed model to account for rescue medication required during the study.

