5.1. Analysis of primary outcome

The log-transformed 24-hour proteinuria values will be analyzed by a mixed-effects general linear regression model with treatment and period as fixed factor and patients (nested in sequence) as a random factor. This type of model, which accounts for repeated observations within individuals (measurement occasion at level one, individuals at level two) will allow us to estimate the treatment effect (estimated by restricted maximum likelihood). We will also explore the period-specific treatment effect adding in the model the interaction between the treatment and period covariates. If the baseline characteristics will be considerably different across the three regions included (Malaysia, North America, Europe) we shall consider to include region as a layer in the multilevel model fitted or as fixed effect covariate. We will also analyse the log-transformed 24-hour albuminuria values (a specific protein using the same model as described above).

The change in secondary outcomes, mGFR, eGFR, body weight and systolic blood pressure will be analyzed by the same model as showed for the proteinuria outcome.

In general, the models employed will be:

$$y_{it} = \beta_{0i} + \beta_1 Treat_{it} + \beta_2 Period_{it} + \beta_3 Interaction + \varepsilon_{it}$$

$$\beta_{0i} = \beta_0 + u_{0i}$$

$$\varepsilon_{it} \sim N(0, \sigma_\varepsilon^2)$$

Where y_{it} is the outcome for the individual i at time point t , β_{0i} is the intercept for individual i comprised of a sample-average fixed effect β_0 and an individual effect u_{0i} and ε_{it} is the residual error.

Complete case analyses, that is analysing records that present the whole set of information (outcome and covariates) for every visit of the patients will be performed. Patterns of missing data (for the outcomes and the covariates) will be reported. If the proportion of missing records is higher than 5% and/or we will suspect of particular missing mechanisms we will impute the missing values by multiple imputation using the full conditional specification.

Further, if there will be baseline measurements that are missing we will use the values measured at the screening visit: we will document the frequency of this imputation.

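### SAP section 5 and protocol 9.3 do not confine their independent-samples tests to sequence-group comparisons, so diastolic pressure, the neurohormones and any tested adverse-event proportion lack a clear within-patient analysis

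*SAP*

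**What the plan says.** - **SAP section 5** says, in a paragraph on descriptive statistics covering every study variable: "The means of the normal distributed variables will be compared with the student T-test and non-parametric tests". The non-parametric tests are Mann-Whitney for continuous and chi-square for categorical variables. It does not say which groups are compared or whether the t-test is paired.
- **Protocol 9.3**, headed as dealing with other study parameters, repeats this: "non-parametric tests (Mann-Whitney U-test for continued and Chi-Square test for nominal variables) will be used" for variables that are not normally distributed. Protocol 7.1.3, under the same title, lists "Number of hypoglycaemic episodes", serious adverse events and drug-related adverse events.
- **SAP 5.1** gives proteinuria and albuminuria a mixed model with patient as a random effect, and then says: "The change in secondary outcomes, mGFR, eGFR, body weight and systolic blood pressure will be analyzed by the same model" as proteinuria. Diastolic pressure and the neurohormones are not in that list, although SAP 2.2 makes both secondary objectives.
- **Protocol 9.2** puts GFR, systolic pressure and the neurohormones in the mixed model. It also leaves out diastolic pressure.
- **SAP 5.3** uses the primary model for the protein:creatinine and albumin:creatinine ratios, and McNemar and/or Mainland-Gart tests for responder proportions.
- **SAP section 6** summarises safety by counts and percentages and names no test.
- **SAP Table 7** plans a dapagliflozin-minus-placebo difference with a p-value for the secondary outcomes.

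**The concern.** Every patient contributes an observation under each treatment, so the two sets of values are paired. Mann-Whitney and chi-square treat them as coming from different people, which discards the within-patient control for which the crossover was chosen. Diastolic pressure and the neurohormones are due a p-value in Table 7, yet the only tests the SAP's text could be said to supply for them are those in section 5. Hormone concentrations are often skewed (an assumption here; the documents do not say), and the section 5 rule sends skewed variables to Mann-Whitney. At stake is the power to see real effects on these secondary outcomes and, if event proportions are tested by chi-square, some of the ability to detect harm. There is also an analyst's choice left open: the SAP does not say whether the section 5 tests or the 5.1 model governs a variable that is not listed.

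**Working it through.** **1. The plan's own sizing uses the pairing.** SAP 3.2 states that "50 patients completing the study would provide 80% power to detect a 25% reduction in albuminuria", with "delta=0.288 on the log-transformed proteinuria scale". Protocol 3.4 names a paired t-test. With two-sided alpha 0.05, a difference of 0.288 and 0.7 taken as the SD of the within-patient difference, a noncentral-t calculation needs 49 patients and gives 81.4% power at 50. The stated figure is reproduced.

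**2. Effect of ignoring the pairing.** For n patients measured under both treatments, with SD σ under each and within-patient correlation ρ:
- correct standard error of the mean difference = σ√(2(1−ρ)/n)
- standard error from an independent-samples analysis = σ√(2/n)
- ratio k = 1/√(1−ρ)
- actual alpha of a nominal 5% test = 2[1−Φ(1.96k)]
- power where the paired analysis has 80% = Φ(1.96 + 0.84 − 1.96k) = Φ(2.80 − 1.96k)

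For example, at ρ = 0.4: k = 1/√0.6 = 1.291; 1.96 × 1.291 = 2.530; alpha = 2[1−Φ(2.530)] = 1.1%; power = Φ(2.80 − 2.53) = Φ(0.27) = 61%.

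The documents give no correlation for diastolic pressure, the hormones or event proportions, so ρ is assumed over a range:

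| Assumed ρ | SE ratio k | Actual alpha | Power where paired gives 80% |
|---|---|---|---|
| 0.2 | 1.12 | 2.8% | 73% |
| 0.4 | 1.29 | 1.1% | 61% |
| 0.6 | 1.58 | 0.2% | 38% |
| 0.8 | 2.24 | below 0.01% | 6% |

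The formulas are large-sample results for means. For Mann-Whitney and chi-square they are a guide.

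**3. Check by simulation, for illustration only.** If 0.7 is read as the total SD of log proteinuria and 0.475 as the within-patient SD, ρ = 1 − 0.475²/0.7² = 0.54. With 50 patients the standard errors are 0.7√(2/50) = 0.140 and 0.475√(2/50) = 0.095, a ratio of 1.47. In 20,000 simulated trials (6,000 for Mann-Whitney):
- Rejection under no effect: unpaired t-test 0.43%, Mann-Whitney 0.6%.
- Power at 0.288: unpaired t-test 54.6%, Mann-Whitney 51%, paired t-test 84%.
- Unpaired t-test between the two sequence groups in period 1, where patients are independent: rejection under no effect 5.2%, as it should be.

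**4. Which variables are exposed.**

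| Variable | Method named |
|---|---|
| Proteinuria, albuminuria, mGFR, eGFR, weight, systolic pressure | Mixed model (SAP 5.1) |
| Protein:creatinine and albumin:creatinine ratios | Primary model (SAP 5.3) |
| Responder proportions | McNemar and/or Mainland-Gart (SAP 5.3) |
| Neurohormones/biomarkers | Mixed model in protocol 9.2; not in the SAP 5.1 list |
| Diastolic pressure | No model in SAP 5.1 or protocol 9.2 |
| Hypoglycaemia, SAEs, drug-related AEs | Protocol 9.3 tests; counts only in SAP section 6 |

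The last three rows are the exposure.

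**The case against.** The strongest reply is that section 5 of the SAP never assigns these tests to dapagliflozin versus placebo. The preceding paragraph describes baseline by sequence group, where independent-samples tests are valid. The sentence that follows says treatment effects are adjusted for period only, which none of the named tests can do. SAP 5.1 also writes out its model in general form, so an analyst might well apply it to every continuous outcome.

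Much of this stands. A reader might infer that unpaired tests are the plan's default for all between-treatment comparisons, and that every variable outside the mixed-model list is affected. The documents do not support that. No comparison groups are named, the t-test is not called unpaired, responder proportions and the creatinine ratios have within-patient methods, SAP safety is untested, and protocol 9.2 models the neurohormones. A reader might also carry the proteinuria figures (ρ = 0.54, power falling from 84% to about 55%) over to the exposed variables. Those figures belong to an outcome that has a mixed model. They also rest on a reading of the SDs that gives 84.4% power at 50 patients, not the stated 80%.

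The baseline-only reading does not dispose of the point, however. Protocol 9.3 carries the same tests under a title that 7.1.3 attaches to outcomes arising on treatment. The SAP only describes baseline by sequence and puts the tests in a separate paragraph of wider scope. SAP Table 1 sets out baseline in dapagliflozin and placebo columns, so the intended groups are unclear even there.

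**Conclusion.** Wrong as written, limited to secondary and other outcomes. Both documents name independent-samples tests without confining them to independent groups. In the SAP, diastolic pressure and the neurohormones have no other named analysis, and under protocol 9.3 the same tests reach adverse-event and hypoglycaemia proportions. Used between treatments, they would give standard errors 1.12 to 2.24 times too wide for an assumed ρ of 0.2 to 0.8, with actual alpha from about 2.8% to below 0.01%. This assumes positive correlation and complete pairs. The result is then conservative: lost power, with no excess of false positives. For rare events the within-patient correlation may be close to zero and the loss small. The primary analysis and the outcomes with a named within-patient method are not affected.

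**What to change.** 1. In SAP section 5 and protocol 9.3, state that the Student t, Mann-Whitney and chi-square tests serve only comparisons between sequence groups.
2. Add diastolic pressure and the neurohormones/biomarkers to the SAP 5.1 mixed model (period fixed, patient random), with skewed hormones analysed on the log scale. This also brings the SAP into line with protocol 9.2 for the neurohormones.
3. If the proportion of patients with an adverse event or hypoglycaemia is tested between treatments, use the paired methods already in SAP 5.3: McNemar, or Mainland-Gart where the period effect matters. Otherwise say that safety is descriptive only, as SAP section 6 implies.

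The cost is a few sentences and a few lines of code. No new data, visits or patients are needed. The change should be dated before the treatment codes are opened.
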